4.3 Objectives

The project emphasizes evaluation of the clinical utility of pharmacotherapy with Vivitrol (VI) or Vivitrol + PN (PNV) in comparison to a drug education (DE) condition. Descriptive statistics will provide an overall assessment of the implementation of the protocol. The aims of this project include:

Aim 1: Assess the feasibility and clinical utility of a 24-week protocol of long-acting naltrexone (by intramuscular *injection*; VI) provided with and without a PN component (VI, PNV). Measures include side effects, adverse events, retention, and acceptance of the procedures by participants and clinicians. Acceptance will also be assessed among correctional staff.

Aim 2: Examine the effectiveness of Vivitrol provided with and without a PN component (VI, PNV) for its ability to prevent relapse to illicit opioid use, reduce drug-related criminal activity, curtail engagement in HIV-risk behaviors, and increase employment compared to a group receiving only drug education (DE) to assist in relapse prevention after release from jail. The VI and PNV groups will receive VI monthly for the entire 6-month intervention phase. Th PNV group will be provided with PN for 3 months to provide assistance in accessing community treatment after release from jail. Primary measures include DSM-5 diagnosis at time to relapse (defined as self-report of daily opioid use for one week), protocol adherence, and opioid-negative urine samples during the study.

Aim 3: Collect cost data using the Drug Abuse Treatment Cost Analysis Program (DATCAP) and estimate savings from reduced drug use, reduced criminal activity and re-incarceration, and increased employment. Data will support benefit-cost and cost-effectiveness analyses of depot pharmacotherapy with Vivitrol for released offenders with opioid use disorders.

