4.3.1 Primary Objectives

The primary objective is to compare outcomes of the three intervention groups, measured a The opioid use and DSM-5 diagnosis of opioid use disorder via modified CIDI-2 Substance Abuse Module at 6-months post-intervention.

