10.0 STATISTICAL ANALYSES

The project emphasizes evaluation of the clinical utility of Vivitrol in jail inmates as compared with a Drug Education condition (DE), while descriptive statistics will provide an overall assessment of the implementation of the protocol.

Analyses will include an Intent-to-treat (ITT) design such that all randomized participants who received at least one dose of medication (VI, PNV), or received at least one session of drug education (DE) will be included who did not violate the protocol in a way that could potentially affect the efficacy results. Participants will be excluded from the Protocol Population (PP) if:

- 1. concomitant medication that is known to have significant clinical effect on primary or secondary endpoints was administered.
- 2. Violations of the inclusion or exclusion criteria are judged to affect the efficacy evaluations.

Subjects in the PP population will be allocated to treatment groups in the analysis based on the actual treatment they received. If there is substantial difference between the ITT population and the PP population, all analyses described below will be performed using only subjects in this group.

All statistical tests will be performed using two-sided .05 significance levels, unless otherwise stated. All comparisons between treatments will be reported with parameter estimates and 95% confidence intervals. For parameters measured at baseline and subsequently, the variables of interest are changes from baseline.

Post-baseline variables will not be imputed; estimates can be obtained using the hierarchical models specified below under the assumption of missing at random. For the primary outcome measure, diagnosis at six months, subjects who have dropped out for whatever reason will be considered to retain the diagnosis. Other outcome measures for which data are missing will be imputed using multiple imputation methods. Sensitivity analyses will repeat specific analyses using permutation tests of at least 1000 samples.

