10.3 Power and Sample Size

With the primary focus of this study on the feasibility and clinical utility of the two pharmacotherapies, the study is not powered to be an exhaustive comparison but to parsimoniously enable preliminary characterization of outcomes that will be needed to inform a future, larger scale multi-site trial. We expect that a baseline sample of 150 participants with 50 participants per condition will yield a final aggregate sample of approximately 120 participants. assuming 10-20% dropout. (Our similar studies have had 85-90% follow-up rates.) Thus, a final evaluable sample size of 120 participants would permit detection of a medium-large effect size (~.60) between conditions for some of the outcome variables (at ~.70 power) and .5 effect size (at .80 power) for others. For example, we expect that the measure "time to first opioid use" will be markedly different among the three groups, given the difference given the expected relapse among the no-medication group. Over time, the total number of opioid-free urine results is expected be greater among the VI participants, who are likely to show less dropout and better long-term retention compared to the DE group. Our selection of the effect size is based on effects found in the literature for Vivitrol when compared against placebo, and is consistent with both Cohen (1988) and with more recent guidance; for example, Lipsey and Wilson (1993) did a meta analysis of 302 meta-analyses that included over 10,000 studies and found that the average effect size was .5, adding support to Cohen's recommendation that selection of the effect size of .5 is appropriate (Bausell & Li, 2002).

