10.4.2 Primary Statistical Analysis of the First Primary Outcome Measure

A mixed effects logistic regression will used to model the binary primary outcome measure; the diagnosis of opioid use disorder at six months post treatment. are modeled as a linear combination of predictor variables. A logit link function will be used to link subject covariates to the probability of success There will be two levels in the model: within sites and between sites. The model will included treatment, cluster (site) and baseline covariates as fixed effects and subject as a random effect. Indicator variables will identify whether a subject has received XR-NTX, methadone and a behavioral intervention (PN.) Site by treatment interactions will be included in the model. Interactions that are statistically significant at the 10% level will be investigated and may imply that analyses of individual sites is required. In this case, relevant contrasts will be performed within the sites.

Additional covariates will include age, gender, whether a subject had prior methadone maintenance treatment and baseline self-reported cocaine use. Other possibilities mediating

factors include opioid dependence severity at baseline, concurrent cocaine or alcohol and/or benzodiazepine misuse, and homelessness.

SAS PROC Mixed will be used to perform the analysis. The coefficients in the model will be estimated by generalized least squares (GLS), with covariance parameters estimated by restricted maximum likelihood (REML). Standard errors of the parameter estimates will be computed using the model. This procedure assumes that missing observations are ignorably missing or missing at random (MAR).

The primary contrast is a comparison of the probability of a DSM-5 Opioid Use Disorder Diagnosis at 6 months for those on medication versus those receiving enhanced treatment as usual (etau.) The contrast will utilize XR NTX data from both the NYU and UCLA and Interim Methadone data from FRI; the medication plus PN treatment arm will not be included.

Descriptive statistics will examine feasibility issues of the pharmacotherapy, analyzing AEs, side effects, and patient and clinician acceptance, and reasons for early termination or post-randomization refusal of assigned condition. Single-point, between-group comparisons of these measures can be tested using t-tests or ANOVAs for continuous variables and chi-square for binary measures.

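### The only contrast designated primary pools NYU and FRI data and omits the PNV arm, so no comparison within this trial is primary

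*Combined protocol and SAP*

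**What the plan says.** - **Primary contrast (Section 10.4.2).** The probability of a DSM-5 opioid use disorder diagnosis at six months, medication against enhanced treatment as usual. The data are "XR NTX data from both the NYU and UCLA and Interim Methadone data from FRI; the medication plus PN treatment arm will not be included".
- **Model (Section 10.4.2).** Mixed logistic regression with site and treatment as fixed effects, indicators for XR-NTX, methadone and PN, and site-by-treatment interactions. If an interaction is significant at 10%, the plan may look at sites separately: "In this case, relevant contrasts will be performed within the sites".
- **Objective (Section 4.3.1).** "The primary objective is to compare outcomes of the three intervention groups". Aim 2 in Section 4.3 sets Vivitrol with and without PN against drug education.
- **Design (Sections 7.3, 5.5 and 7.6.1).** Allocation is 1:1:1 to VI, PNV and DE. Recruitment, data collection and treatment take place at one county jail system and the University of New Mexico. DE is the enhanced treatment-as-usual arm.
- **Sample size (Section 10.3).** "a baseline sample of 150 participants with 50 participants per condition will yield a final aggregate sample of approximately 120 participants". No figure is given for any other study.
- **Reporting (Section 10.0).** Tests are at two-sided .05 unless otherwise stated. "All comparisons between treatments will be reported with parameter estimates and 95% confidence intervals".

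**The concern.** The plan names its primary contrast once, and that contrast does not match the trial. It leaves out one of the three randomised arms. It also brings in methadone recipients, although no arm here receives methadone, and it relies on two data sources that the text does not describe. The quantity estimated is the effect of XR-NTX or methadone across three sources, whereas the objectives concern Vivitrol in this population, with and without navigation.

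Two things are at stake. The stated primary result cannot be computed from this trial's data alone. And the comparisons that answer Aim 2 carry no primary status, so the plan does not fix which of them is the headline result or how error is shared between them. Section 10.3 says the results should inform a larger multi-site trial, which would need clear VI and PNV estimates.

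**Working it through.** **1. Contrast against trial**

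| Feature | Primary contrast (10.4.2) | This trial |
|---|---|---|
| Medication | XR-NTX or interim methadone | XR-NTX only |
| Arms used | Medication without PN; enhanced treatment as usual | VI, PNV, DE |
| Sources | NYU, UCLA, FRI | One jail system and UNM, led from UCLA |
| Sample size | None given | 150 randomised, about 120 evaluable |

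NYU and FRI appear only in Section 10.4.2. Their designs, eligibility rules and sizes are not given. Nor does the text say whether the treatment-as-usual comparators come from all three sources or only from DE.

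**2. Share of this trial in the contrast (illustration)**

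The other sources' sizes are unknown. Assume that each contributes N medicated participants beside this trial's 50 in VI; the VI share is then 50/(50 + 2N). For N = 40 it is 50/130 = 38%; for N = 50, 50/150 = 33%; for N = 100, 50/250 = 20%. These are head counts, not model weights.

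**3. The plan's own power figures**

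- Evaluable total: 150 × (1 − 0.20) = 120, which reproduces. That is 40 per arm if dropout is equal.
- Two-sample t-test, 40 per arm, two-sided .05: power is 0.755 at d = 0.60 (the plan says about .70) and 0.598 at d = 0.50 (the plan says .80). Neither reproduces. The finding here does not depend on this, but it bears on the restatement asked for below.

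**4. Cost of two within-trial primary contrasts (VI and PNV, each against DE)**

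Unadjusted, the familywise error would be 1 − 0.95² = 0.0975 if the tests were independent. They share DE, so the true figure is somewhat lower. Under Holm's procedure the strictest level is .05/2 = .025.

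Detectable d at 80% power, normal approximation: d = (z for 1 − α/2, plus z for 0.80) × √(2/n), with n = 40.

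- α = .05: (1.960 + 0.842) × √(2/40) = 0.626; exact t, 0.634.
- α = .025: (2.241 + 0.842) × √(2/40) = 0.689; exact t, 0.701.

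Power at d = 0.60, exact t: 0.755 at .05 and 0.655 at .025. The first contrast in a fixed order keeps the .05 figures.

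**5. Same cost for the diagnosis**

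Section 10.0 counts dropouts as retaining the diagnosis, so up to 50 per arm may be analysed. This is an upper bound, because Section 10.0 also removes people with violations that could affect efficacy. The documents give no diagnosis rates; DE rates of 50% to 90% are assumed. With the pooled-variance formula, n = [z₁√(2p̄q̄) + z₂√(p₁q₁ + p₂q₂)]²/Δ², where z₁ is for 1 − α/2 and z₂ for 0.80:

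| DE rate | Detectable Δ, α = .05 | Detectable Δ, α = .025 |
|---|---|---|
| 0.5 | 0.267 | 0.291 |
| 0.6 | 0.276 | 0.303 |
| 0.7 | 0.275 | 0.303 |
| 0.8 | 0.260 | 0.289 |
| 0.9 | 0.227 | 0.255 |

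The range moves from about 23–28 points to about 26–30 points.

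**The case against.** The best defence is that a coordinated analysis across three related studies was intended and that the plan supports it. Much of this stands. A reader might infer that there is no pooling plan, but Section 10.4.2 gives one: site effects, treatment indicators, site-by-treatment terms and a 10% trigger for looking within sites. What is missing is a description of the NYU and FRI data. Even that is judged on text in which the schema in Section 3.0 is not shown and some pages are absent.

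A reader might also infer that VI and PNV effects in this trial cannot be obtained, or that their significance level would be chosen after the data are seen. Neither follows. The effects are estimable, Section 10.0 sets two-sided .05 throughout, and nothing says that the choice is deferred. The gaps are primary status and a multiplicity rule. The within-site contrasts do not fill them: they depend on an interaction test and are not called primary.

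It is tempting to count four missing contrasts, two comparisons on each of two primary outcomes. The documents do not settle that. Sections 2.4 (Analyses), 6.1 and 10.1 call opioid use primary. Sections 4.3.2, 6.2 and 10.2 list self-reported opioid-use days as secondary, and Section 10.0 speaks of a single primary outcome measure. Section 4.3.1 would also allow an overall three-group test or all three pairwise contrasts; VI and PNV against DE is the reading closest to Aim 2.

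Finally, Section 10.3 presents the study as preliminary and not powered for exhaustive comparison. That bears on how strict the multiplicity rule should be. It does not justify a primary contrast that omits a randomised arm and needs outside data.

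**Conclusion.** The point holds and must be fixed. The sole designated primary contrast needs data from outside the trial, mixes in a drug that the trial does not give, and excludes PNV. It therefore cannot be produced from this trial and does not answer the stated primary objective. This is a conflict within the document, and it does not depend on any power calculation.

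The conclusion is limited to designation. It does not say that the pooled analysis is invalid or lacks a model, or that the within-trial effects are lost. The power figures assume 40 evaluable per arm with equal dropout; the diagnosis figures assume at most 50 per arm and the DE rates stated above.

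**What to change.** In Section 10.4.2:

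1. Designate the within-trial contrasts on the six-month diagnosis as primary. VI against DE and PNV against DE, by assigned arm, follow Aim 2. State a multiplicity rule in advance, for example Holm's procedure or a fixed order; the choice is the sponsor's.
2. Report PNV against VI with its estimate and 95% confidence interval.
3. Fit these contrasts in this trial's data by logistic regression on arm and baseline covariates, without the methadone and site terms.
4. Keep the NYU/UCLA/FRI contrast as a separately labelled cross-study analysis. Describe its sources: design, eligibility, size and which comparators enter.

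Elsewhere, reconcile whether past-30-day opioid-use days are primary or secondary. If primary, name the same contrasts for them. Restate the power statement in Section 10.3 to match the rule chosen, since the worst case under Holm at d = 0.60 falls below its figure of about .70.

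No new data are needed. The cost is the loss of power per contrast shown above.

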10.4.3 Economic Analysis (Aim 3)

The costs of the Vivitrol will be estimated using the Drug Abuse Treatment Cost Analysis Program (DATCAP_[d1]; French, 2003b). The DATCAP is a data collection instrument and interview guide designed to estimate the costs of substance abuse treatment and related interventions. Because the DATCAP organizes cost data across standard categories of resources (e.g., personnel, buildings and facilities, supplies and materials, and miscellaneous), it can be used for other types of interventions including pharmacotherapies. Cost data will be obtained to calculate the total annual cost of Vivitrol and the average per-client cost. We will not include any costs specific to research conducted under this study. To ascertain the full economic impact of Vivitrol, cost data will be compared to changes in key clinical measures of effectiveness (e.g., time to relapse, days of abstinence, re-arrest) to estimate cost-effectiveness ratios. Cost-effectiveness analysis (CEA) is inherently an incremental analysis that compares doing a little more or a little less of something to capture marginal variations in costs and effectiveness across interventions (Gold et al., 1996). Differences in program cost are divided by differences in program effectiveness to calculate incremental cost-effectiveness ratios (ICERs). One can then compare the ratios of cost to outcome for two or more alternative programs (in this case Vivitrol) to determine which programs are relatively more cost-effective (i.e., have a lower cost-effectiveness ratio). The more expensive pharmacotherapy will be directly assessed to see if the additional cost generates greater effectiveness across the key outcomes of interest. As an alternative approach to examining the full economic impact of this pharmacotherapy, we will estimate the economic benefits associated with reductions in criminal activity and criminal justice system costs, improved employment, and reduced health care use. The difference between economic benefits and intervention costs represents the net economic benefits of the interventions. The primary objectives of the benefit analysis are to identify important economic outcomes for Vivitrol, convert these outcomes into dollar equivalents, and estimate the therapy's total and domain-specific economic benefits. Decreases in some measures between baseline and follow-up, such as number of arrests, represent improvement while other measures, such as hours worked, show improvement with increases. Benefit-cost analysis (BCA) expresses results as a benefit-cost ratio (benefit divided by cost) or a net benefit estimate (benefit minus cost) and considers an intervention costbeneficial if the benefit-cost ratio exceeds unity or if the net benefit estimate is positive. In

summary, we will be able to describe the economic impact of Vivitrol in terms of both costeffectiveness and net economic benefits.

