2.4 Analyses

The primary outcomes include opioid use and DSM-5 diagnosis of opioid use disorder via modified CIDI-2 Substance Abuse Module at 6-months post-intervention. Opioid use will be computed from the Timeline Follow-Back (TLFB) as the number of days of self-reported opioid use in the past 30 days at the 6-month assessment. The cost analysis will measure and value resources associated with VI, including medical personnel (physician/nurses), labs, and medications. To ascertain cost-effectiveness ratios of VI and PNV, cost data will be compared to changes in key clinical measures of effectiveness.

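### Equating more cost-effective with a lower ratio is not valid when ICERs differ in sign, and no interval method suited to a ratio is named

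*Combined protocol and SAP*

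**What the plan says.** The economic evaluation is Aim 3 (section 4.3) and is specified in section 10.4.3. The ratio is defined there: "Differences in program cost are divided by differences in program effectiveness to calculate incremental cost-effectiveness ratios (ICERs"). The next sentence begins "One can then compare the ratios of cost to outcome for two or more alternative programs" and gives the purpose as "to determine which programs are relatively more cost-effective (i.e., have a lower cost-effectiveness ratio"). It is followed by: "The more expensive pharmacotherapy will be directly assessed to see if the additional cost generates greater effectiveness across the key outcomes of interest".

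The effectiveness measures are given by example: "e.g., time to relapse, days of abstinence, re-arrest". The first two improve upwards and the third improves downwards. Section 2.4 (Analyses) names the arms concerned: "To ascertain cost-effectiveness ratios of VI and PNV, cost data will be compared to changes in key clinical measures of effectiveness".

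Section 10.4.3 also plans a separate benefit-cost analysis of outcomes converted to dollars, which "considers an intervention costbeneficial if the benefit-cost ratio exceeds unity or if the net benefit estimate is positive". On uncertainty, the only relevant text is the general rule in section 10.0: "All comparisons between treatments will be reported with parameter estimates and 95% confidence intervals".

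Section 10.4.3 states no dominance rule, no willingness-to-pay range, no common direction of coding for the cost-effectiveness measures, and no interval method for an ICER.

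**The concern.** A ratio of two differences loses information about sign. It is negative when an arm is cheaper and better, and also when it is dearer and worse. A lower-is-better ordering therefore cannot separate the best case from the worst, and it places both ahead of any arm that buys benefit at extra cost. Re-arrest adds a second problem that needs no sampling error: a dearer arm that reduces re-arrest has a negative ratio, and among such arms the lowest ratio belongs to the one that pays most per arrest averted.

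Uncertainty is a separate matter. An ICER has no well-behaved standard confidence interval when its denominator may be close to zero, so a general instruction to report 95% intervals does not tell the analyst what to compute.

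The stakes are the Aim 3 conclusion. Sections 4.1.1 and 4.1.2 argue that adoption by correctional agencies may depend on cost evidence and on established net economic benefits. A reversed or falsely firm ordering of VI and PNV would matter to those readers.

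**Working it through.** The economic section states no numerical result, so there is nothing to reproduce. Dollar amounts and the value per unit of effect below are assumptions for illustration.

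**1. Sign check.** ICER = ΔC/ΔE. Net monetary benefit (NMB) = λ·ΔE − ΔC, with assumed λ = $400 per unit, and effect coded so that higher is better.

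| Case | ΔC ($) | ΔE | ICER | NMB ($) |
|---|---|---|---|---|
| Dearer, much better | 6,000 | +20 | +300 | 400×20 − 6,000 = +2,000 |
| Dearer, slightly better | 6,000 | +5 | +1,200 | −4,000 |
| Dearer, slightly worse | 6,000 | −5 | −1,200 | −8,000 |
| Dearer, much worse | 6,000 | −20 | −300 | −14,000 |
| Cheaper, better | −500 | +10 | −50 | 400×10 + 500 = +4,500 |

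Taken alone, the lower-ratio ordering puts the dearer, slightly worse program first (−1,200) and the cheaper, better one third (−50), behind both dominated programs. NMB puts the cheaper, better program first and the two dominated ones last.

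**2. Re-arrest, uncoded.** Take two arms each $6,000 dearer than drug education (DE). A difference of −2 arrests gives 6,000/−2 = −3,000; a difference of −1 gives 6,000/−1 = −6,000. The lower ratio belongs to the arm with half the improvement. The cost per arrest averted is $3,000 and $6,000, so the correct order is the reverse.

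**3. Chance of a wrong-sign denominator.** Section 10.3 gives 150 randomised and about 120 evaluable in three equal arms, so 50 or 40 per arm. It plans on standardised effects of about 0.5 to 0.6. For a true difference of d SD, SE = √(2/n), which is 0.224 at n = 40 and 0.200 at n = 50. Then P(estimated ΔE < 0) = Φ(−d/SE).

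| True d | n = 40 | n = 50 |
|---|---|---|
| 0.1 | 0.327 | 0.309 |
| 0.2 | 0.186 | 0.159 |
| 0.3 | 0.090 | 0.067 |
| 0.5 | 0.013 | 0.006 |
| 0.6 | 0.004 | 0.001 |

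**4. Effect on the ordering.** This is a simulation of 400,000 trials with 40 per arm, both ICERs taken against a shared DE arm, and assumed fixed extra costs of $6,000 (VI) and $8,000 (PNV). The table shows how often the lowest ICER belonged to an arm estimated as less effective than DE.

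| True effects, VI / PNV (SD) | Share of trials |
|---|---|
| 0.5 / 0.5 | 2.4% |
| 0.5 / 0.2 | 19% |
| 0.2 / 0.2 | 29% |
| 0 / 0 | 67% |

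**5. Interval for the ratio.** A Fieller 95% set is unbounded when the estimated ΔE lies within 1.96 SE of zero. At 40 per arm, a difference of 0.2 SD is 0.2/0.224 = 0.89 SE from zero, and one of 0.5 SD is 0.5/0.224 = 2.24 SE, only just beyond the limit.

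**The case against.** A reader might infer that the plan will declare a dearer, less effective arm the most cost-effective. The documents do not support that, for four reasons.

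- The sentence immediately after the lower-ratio wording asks whether the extra cost buys extra effect, and a dominated arm would fail that check on inspection. This stands as a guard, but only in part. It attaches no consequence to failing, does not amend the ordering, and speaks of a dearer pharmacotherapy when VI and PNV share the same drug and differ by navigation. It also does nothing about the direction of re-arrest.
- The ordering appears in a descriptive sentence rather than a binding algorithm, and the ratios it mentions could be average ratios, which are positive when cost and outcome are positive. The ambiguity is real. However, the preceding sentence defines ICERs, and the section sets costs against changes in measures that include re-arrest, so the reversal in step 2 can arise on either reading.
- The benefit-minus-cost analysis does not have the sign problem, and in that context the section recognises that fewer arrests is an improvement. Both points are correct, but that analysis is presented as an alternative. Neither its criterion nor its sense of direction is carried into the cost-effectiveness comparison.
- Section 10.0 asks for 95% confidence intervals, so it would be too strong to say that the plan ignores sampling uncertainty. What is missing is a method that works for a ratio.

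It would also be wrong to trace the sign problem to the missing intervals. It comes from the absent dominance and direction rules, and adding intervals alone would not cure it.

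**Conclusion.** The concern holds in this limited form. As worded, the lower-ratio ordering is invalid for ICERs of mixed sign, so a dominated arm could be ranked first. On uncoded re-arrest it reverses the order of dearer beneficial arms whatever the sample size. The check that follows it is a partial safeguard.

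The missing interval method is a second, separate gap. Its size depends on the effect. At the planned 0.5 SD the wrong-sign risk is about 1% (0.6% at 50 per arm, 1.3% at 40) and matters little. At an assumed 0.2 SD it is about 19% at 40 per arm, which is material. PNV against VI is where this is most likely to apply: section 10.3 bases its effect size on Vivitrol against placebo and plans none for adding navigation. The 0.2 SD is therefore an assumption, as are all dollar figures used here.

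The primary clinical outcomes are unaffected. Section 10.3 describes the trial as preliminary, which limits the consequence, but Aim 3 is one of three stated aims and the correction is cheap.

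**What to change.** Amend section 10.4.3 before any economic data are analysed:

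- Code every effectiveness measure so that higher is better, for example arrests averted in place of re-arrests.
- Order DE, VI and PNV by mean cost and apply dominance before any ICER is formed.
- Replace the lower-ratio ordering with incremental net benefit (willingness to pay × effect difference − cost difference) over a stated willingness-to-pay range for each measure, and name the contrasts, including PNV against VI.
- Report bootstrap 95% intervals for incremental cost, effect and net benefit, with acceptability curves over the same range.
- Show an ICER only where both cost and effect are higher than the comparator's.

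The cost is some SAP wording and bootstrap programming, with no new data. The downside is a less definite economic conclusion, because the result becomes a probability that varies with willingness to pay instead of a single ordering.
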